### ***3.4.3 Hammersmith Functional Motor Scale – Expanded***

All subjects who have maintained a CHOP INTEND total score of  $\geq 50$  for two consecutive study visits will be evaluated using the Hammersmith Functional Motor Scale Expanded (HFMSE). This evaluation will be performed in addition to the CHOP INTEND. Since the data is only collected for a subset of patients, the data will be provided in a data listing.

## **3.5 Pharmacokinetic Analyses**

CSF and plasma samples will be collected at protocol designated times for ISIS 396443 pharmacokinetic assessments from all treatment groups (cohorts).

### ***3.5.1 CSF Concentration Data***

CSF concentrations of ISIS 396443, along with the scheduled (nominal) and actual samples times (i.e., time from IT dosing) will be listed (when applicable) for each patient, treatment group (cohort), nominal dose, and day. Differences between scheduled and actual sampling days will also be listed for all patients. Percent differences between actual administered dose and nominal dose will also be listed.

CSF concentrations below the lower limit of quantification (LLOQ) will be indicated by “BLQ”. For the purpose of calculating typical descriptive statistics (n, mean, SD, %CV, geometric mean, geometric %CV, median, minimum, and maximum) for CSF concentrations, all BLQ values will be set to zero. Mean CSF concentrations that are BLQ will be presented as BLQ, and the SD and %CV will be reported as not applicable. Summary statistics of the ISIS 396443 CSF concentrations will be tabulated by treatment group (cohort), nominal dose, day, and scheduled time point. At the discretion of the pharmacokineticist and/or biostatistician, samples may be excluded from descriptive statistics if there are large deviations between scheduled and actual sampling days or times, or large deviations between actual dose and nominal dose.

ISIS 396443 CSF concentration versus time (actual) profiles from Day 1 to Day 673, for each patient, as well as the mean ( $\pm$ SE) CSF concentration versus time (scheduled) profiles for each treatment cohort, will be presented graphically. Samples may be excluded from the mean plots if there are large deviations between scheduled and actual sampling times, or large deviations between actual dose and nominal dose.

Due to the limited CSF samples collected no CSF pharmacokinetic parameters will be calculated.

### ***3.5.2 Plasma Pharmacokinetics***

#### ***3.5.2.1 Plasma Concentration Data***

Plasma concentrations of ISIS 396443, along with the scheduled (nominal) and actual samples times (i.e., time from IT dosing) will be listed (when applicable) for each patient, treatment group (cohort), nominal dose, and day. Percent differences between scheduled and actual sampling times will also be listed for all patients. Percent differences between actual administered dose and nominal dose will also be listed.

Plasma concentrations below the lower limit of quantification (LLOQ) will be indicated by “BLQ”. For the purpose of calculating typical descriptive statistics (n, mean, SD, %CV, geometric mean, geometric %CV, median, minimum, and maximum) for plasma concentrations, all BLQ values will be set to zero. Mean plasma concentrations that are BLQ will be presented as BLQ, and the SD and %CV will be reported as not applicable. Summary statistics of the ISIS 396443 plasma concentrations will be tabulated by treatment group (cohort), nominal dose, day, and scheduled time point. At the discretion of the pharmacokineticist and/or biostatistician, samples may be excluded from descriptive statistics if there are large deviations between scheduled and actual sampling times, or large deviations between actual dose and nominal dose.

ISIS 396443 plasma concentration versus time (actual) profiles from Day 1 to Day 15 (Cohorts 1 and 2), for each patient, as well as the mean ( $\pm$ SE) plasma concentration versus time (scheduled) profiles for each treatment cohort, will be presented graphically on linear and semilogarithmic scales. Additionally, ISIS 396443 plasma concentration versus time (actual) profiles (Day 1) from 0 to 24 hours for all patients, as well as the mean ( $\pm$ SE) plasma concentration versus time (scheduled) profiles (0 to 24 hours) for each applicable treatment cohort will be presented graphically on linear and semilogarithmic scales. Samples may be excluded from the mean plots if there are large deviations between scheduled and actual sampling times, or large deviations between actual dose and nominal dose.

ISIS 396443 plasma trough (predose) concentration versus time (actual) profiles from Day 1 to Day 673, for each patient, as well as the mean ( $\pm$ SE) plasma concentration versus time (scheduled) profiles for each treatment cohort, will be presented graphically. Samples may be excluded from the mean plots if there are large deviations between scheduled and actual sampling times, or large deviations between actual dose and nominal dose.

#### ***3.5.2.2 Plasma Pharmacokinetic Parameters***

Non-compartmental pharmacokinetic analysis of ISIS 396443 will be carried out on each individual subject data set using Phoenix WinNonlin version 6.0 or higher (Pharsight

Corporation, Mountain View, CA). Plasma pharmacokinetic parameters in each patient (when applicable) will be determined. For calculation of PK parameters, all BLQ values will be set to zero. The following plasma PK parameters will be calculated (when applicable) and based on actual sampling times:

- $C_{\max}$ : the maximum observed drug concentration in plasma.
- $T_{\max}$ : the time at which  $C_{\max}$  occurs.

The following PK parameters may be calculated using actual sampling times where appropriate data exists at the discretion of the pharmacokinetic scientist:

- $AUC_{0-4h}$ : areas under the plasma concentration-time curve from zero time (pre-dose) to 4 hours after IT administration will be calculated using the linear trapezoidal rule.
- Additional partial AUC values (e.g.,  $AUC_{0-24h}$ ) may be calculated depending upon the samples collected during the study and the number of patients for which additional samples are collected via an indwelling catheter, as well as when warranted and at the discretion of the pharmacokinetic scientist.
- Though outlined in the study protocol, apparent terminal elimination half-life ( $t_{1/2}$ ) values will not be determined as the limited post-treatment sampling schedule precludes this evaluation.

Plasma pharmacokinetic parameters (if applicable) will be summarized using descriptive statistics (n, mean, SD, %CV, geometric mean, geometric %CV, median, minimum, and maximum) by treatment cohort, nominal dose, and day.

### **3.5.2.3 *Immunogenicity Analyses***

Immunogenicity (IM) testing (anti-ISIS 396443 antibody positivity), using designated plasma samples collected from each study subject, is planned to be conducted and reported. Initially, designated available immunogenicity plasma samples collected only on Days 1 (predose only), 85 (predose only), 169, 253, 337, 421, 505, 589, and 673 are planned to undergo immunogenicity testing. Plasma samples collected at other time points for ISIS 396443 concentration determinations may also be potentially evaluated for IM testing if of further interest and deemed warranted by the pharmacokinetic scientist. An individual sample result will be designated ‘antibody positive’ based on both positive screening and confirmation assay results (i.e., confirmed positive result), and otherwise will be deemed ‘antibody negative’. A study subject will be given ‘antibody positive’ status if they have at least one confirmed positive sample result at any time during the treatment or post-treatment evaluation periods. A study subject will be given ‘antibody negative’ status if all evaluated IM sample results are antibody negative and they have at least one evaluable IM result from Day 85 or later during the treatment and post-treatment evaluation periods. Otherwise, a study subject will be given ‘antibody inconclusive’ status.

The IM incidence and IM incidence rate at each evaluated study timepoint, and for the overall treatment and post-treatment evaluation period, will be determined and appropriately summarized, by treatment, as the number of and percent (%) of evaluated subjects with antibody negative, antibody positive, and antibody inconclusive status. In addition, in antibody positive study subjects, antibody titers of any antibody positive samples will be reported (listed) and also appropriately summarized across subjects and by treatment (e.g., at each evaluated timepoint, or by observed peak titer values, etc.) at the discretion of the designated study pharmacokineticist and/or statistician.

At this time, antibody positivity in any antibody positive study subjects from this study is not yet planned to be designated as being either 'persistent' or 'transient'. However, the IM results from this study may be evaluated at a later date (and possibly in combination with IM results from other studies potentially involving these patients) to determine these designations. At that time, criteria for persistent versus transient positive antibody responses will also be defined.

When and where warranted, PK and selected safety and efficacy results may be further summarized (stratified) by antibody status (antibody negative vs. positive subjects) and treatment.

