#### **6.2.2 *Laboratory Analytes***

Laboratory measurements of serum chemistry, hematology, urinalysis, coagulation parameters, and plasma antibodies to ISIS 396443 will be performed at the times shown in the Schedule of Procedures (Appendix A). The analytes to be measured are shown in Appendix B.

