### **6.2.10    *Phone Assessments***

Monitoring telephone calls will occur on Study Days 8, 43, 57, 71, 106, 127, 134, 148, 189, 197, 218, 239, 274, 295, 316, 358, 380, 400, 421, 463, 484, 506, 526, 547, 589, 610, 632, 652, 673, 715, 736, 758, 778, 799, 841, 862, 884, 904, 925, 967, 988, 1010, 1030, 1051, 1093, 1114, 1136, 1156, 1177, 1219, 1240, 1262, 1282, 1303, and 1324 (i.e., approximately every 3 weeks between study visits). Changes in concomitant medications and adverse events will be recorded. In addition, information on the subject's ventilator use and SMA disease status will be collected.

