## Appendix A – Schedule of Procedures for ‘Maintenance’ Dosing Period, Visits Only\*

\* Note that monitoring telephone calls will also occur on Study Days 274 ( $\pm 3$ ), 295 ( $\pm 3$ ), 316 ( $\pm 3$ ), 358 ( $\pm 3$ ), 400 ( $\pm 3$ ), 421 ( $\pm 3$ ), 463 ( $\pm 3$ ), 484 ( $\pm 3$ ), 526 ( $\pm 3$ ), 547 ( $\pm 3$ ), 589 ( $\pm 3$ ), 610 ( $\pm 3$ ), 652 ( $\pm 3$ ), 673 ( $\pm 3$ ), 715 ( $\pm 3$ ), 736 ( $\pm 3$ ), 778 ( $\pm 3$ ), 799 ( $\pm 3$ ), 841 ( $\pm 3$ ), 862 ( $\pm 3$ ), 904 ( $\pm 3$ ), 925 ( $\pm 3$ ), 967 ( $\pm 3$ ), 988 ( $\pm 3$ ), 1030 ( $\pm 3$ ), 1051 ( $\pm 3$ ), 1093 ( $\pm 3$ ), 1114 ( $\pm 3$ ), 1156 ( $\pm 3$ ), 1177 ( $\pm 3$ ), 1219 ( $\pm 3$ ), 1240 ( $\pm 3$ ), 1282 ( $\pm 3$ ), 1303 ( $\pm 3$ ), and 1324 ( $\pm 3$ ) (i.e., approximately every 3 weeks)

Study Period	Dosing/Followup									
	D253 Injection ( $\pm 7$ D)			D254	D337 ( $\pm 7$ D)	D379, 505, 631, 757, 883, 1009, 1135, and 1261 Injection ( $\pm 7$ D)			D380, 506, 632, 758, 884, 1010, 1136, 1262	D442, 568, 694, 820, 946, 1072, 1198 ( $\pm 7$ D)
Study Day	Pre-dose	LP	Post-dose			Pre-dose	LP	Post-dose		
Study Drug: LP Injection 		X 					X 			
Vital Signs 	X		4X 	X	X	X		4X 		X
Weight	X				X	X				X
Growth Parameters 	X 				X	X 				X
Physical Examination	X				X	X				X
Ventilator Use	X				X	X				X
Neurological Examination	X		2X 	X	X	X		2X 		X
ECG					X					X 
Safety Labs 	X 				X					X
Immunogenicity 	X 				X					X
CSF Safety 	X					X				
CSF PK 	X					X				
Plasma PK 	X 					X 				X
CHOP INTEND	X 				X	X 				X
HFMSE 						X 				X
CMAP	X 				X					X
Phone Contact									X	
Con Med Recording	X	X	X	X	X	X	X	X	X	X
Adverse Event Collection	X	X	X	X	X	X	X	X	X	X

- 1 Resting blood pressure, pulse, respiratory rate, temperature, and pulse oximetry awake
- 2 Vital signs performed 1, 2, 4, 6 hours after dosing
- 3 Length, weight for age/length, head circumference, chest circumference, head to chest circumference ratio, arm circumference
- 4 Neurological exams at 3 and 6 hours after dosing
- 5 Serum chemistry, hematology, urinalysis panels (see Appendix B for analytes)

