**Legend Text *Continued***

- 12 ECG should be performed on Day 568 only
- 13 Immunogenicity assessments will be performed as deemed necessary on samples collected on other days
- 14 All subjects who have maintained a CHOP INTEND total score of  $\geq 50$  for 2 consecutive study visits will be evaluated using the Hammersmith Functional Motor Scale Expanded (HFMSE) in addition to CHOP INTEND

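### The SAP's antibody-testing days do not match the protocol: three are telephone days with no sample, and all seven marked visits after Day 337 are left off

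*SAP*

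**What the plan says.** Protocol 6.2.2 makes the schedule table binding for antibodies: "plasma antibodies to ISIS 396443 will be performed at the times shown in the Schedule of Procedures (Appendix A". In Appendix A, the loading-period table marks immunogenicity at Day 1 predose, Day 85 predose and Day 169. The maintenance table marks Day 253 predose, Day 337 and the column headed "D442, 568, 694, 820, 946, 1072, 1198". Footnote 13 to that row reads "Immunogenicity assessments will be performed as deemed necessary on samples collected on other days".

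SAP 3.5.2.3 says that testing will initially use samples collected only on Days 1 and 85 (both predose) and 169, then "253, 337, 421, 505, 589, and 673 are planned to undergo immunogenicity testing". Beyond that list it offers one discretionary route: "Plasma samples collected at other time points for ISIS 396443 concentration determinations may also be potentially evaluated for IM testing", if the pharmacokinetic scientist considers it warranted.

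The same SAP section calls a subject antibody negative if every evaluated result is negative and at least one comes from Day 85 or later. It reports status at each tested timepoint and for the treatment and post-treatment period as a whole. It also allows pharmacokinetic, safety and efficacy results to be split by that status.

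**The concern.** The SAP list and the protocol schedule agree up to Day 337 and then diverge. From there the SAP names three days on which no blood is scheduled and omits every visit at which the protocol requires an antibody sample.

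The negative rule makes this matter. It asks only that whatever was tested be negative, with one result from Day 85 onward. If testing in effect ends at Day 505, a response first appearing in the later part of a study that doses to Day 1261 would be missed, and the subject would still be counted as negative for the overall period. The per-timepoint table would show which days were tested. The overall status would not, and neither would any analysis stratified by it.

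**Working it through.** The plan gives no figure to reproduce, so the check compares lists of days.

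**Inputs**
- S, the SAP days (SAP 3.5.2.3): {1, 85, 169, 253, 337, 421, 505, 589, 673}, 9 days.
- A, the marked immunogenicity days (Protocol Appendix A): {1, 85, 169, 253, 337, 442, 568, 694, 820, 946, 1072, 1198}, 12 days. The Day 1352 column is not visible in the copy reviewed, so nothing is concluded about a mark there.
- Telephone days (Protocol 6.2.10 and SAP 1.1): both lists contain the run "421, 463, 484, 506, 526, 547, 589, 610, 632, 652, 673". On the content of a call, the protocol says "Changes in concomitant medications and adverse events will be recorded", and adds ventilator use and disease status. No blood is drawn.
- Dosing days (Protocol 3.1): {1, 15, 85, 253, 379, 505, 631, 757, 883, 1009, 1135, 1261}, 12 doses.
- Scheduled plasma for drug concentration: Protocol Appendix C.

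**Check on reading the table.** The last immunogenicity mark sits in the same column as the last ECG mark. Footnote 12 to the ECG row says "ECG should be performed on Day 568 only", and Day 568 appears only in the heading for Days 442 to 1198. The immunogenicity mark therefore belongs to those seven visits.

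**The nine SAP days against the protocol**

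| SAP day | Contact | Marked in Appendix A | Scheduled sample |
|---|---|---|---|
| 1, 85, 253 | Dosing visit | Yes | Yes |
| 169, 337 | Clinic visit | Yes | Yes |
| 505 | Dosing visit | No | Predose pharmacokinetic plasma only |
| 421, 589, 673 | Telephone | No | None |

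- In both lists: {1, 85, 169, 253, 337}, 5 days.
- In the SAP only: {421, 505, 589, 673}, 4 days, of which 3 have no sample.
- In Appendix A only: {442, 568, 694, 820, 946, 1072, 1198}, 7 of 12 days.

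**Could the visit window explain the telephone days?** 442 − 421 = 21; 589 − 568 = 21; 694 − 673 = 21. The window is ±7 days, so it does not. The SAP list steps by 84 days throughout. Appendix A steps by 84 days to Day 337, then by 105, then by 126. The SAP list looks as though it was never aligned to the current schedule, but that is inference.

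**What the list leaves uncovered**
- Last listed day with a scheduled sample: Day 505, predose.
- Doses given on or after Day 505: {505, 631, 757, 883, 1009, 1135, 1261} = 7 of 12.
- From Day 505 to the last dose: 1261 − 505 = 756 days. To the last marked visit: 1198 − 505 = 693 days.
- If the Day 505 sample is not tested, because it is not an immunogenicity sample, the last tested day is 337, and 7 + 1 (Day 379) = 8 of 12 doses follow it.
- For a subject who completes dosing, no listed day falls after the last dose.

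**The case against.** The best defence is that the SAP text is hedged. It describes an initial round on whatever designated samples are available, so a telephone day is an empty label that produces no wrong result. Appendix A also marks plasma pharmacokinetics at the seven omitted visits, so the discretionary clause could reach all of them, and footnote 13 covers Day 505. Immunogenicity is not a named endpoint in either document. The summary is descriptive in about 20 subjects, stratification by status is optional, and per-timepoint incidence would show which days were tested.

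Part of this stands. The coverage figures describe the initial list, and later testing could shrink the gap. No primary or secondary efficacy result depends on it. But no later round is defined, and a clause that permits testing does not meet a protocol requirement to test. The fallback is also uncertain: Appendix A marks plasma pharmacokinetics at the seven visits, whereas Appendix C lists no blood on any of them. Footnote 13 adds days to the marked ones and does not excuse leaving those out. Nothing creates a sample on a telephone day.

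Three narrower points are fair:
- A subject who stops treatment early may have listed days that are post-treatment, so the absence of post-treatment data applies to those who complete dosing.
- Aligning with Protocol 6.2.2 strictly needs only the Appendix A days. Day 505 and Day 1352/ET are additions.
- The negative rule itself is left alone, so a subject with few results can still be called negative on thin evidence.

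**Conclusion.** The concern holds. The SAP's stated testing days contradict Protocol 6.2.2 and Appendix A. Of the 9 listed days, 3 have no scheduled visit or sample and 1 has a pharmacokinetic sample only. Of the 12 visible protocol immunogenicity days, 7 are missing, which is every one after Day 337. Followed as written, the initial list yields no sample after Day 505, yet it supports an antibody status reported for the whole treatment and post-treatment period.

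This rests on reading the last maintenance column as Days 442 to 1198, which the ECG footnote supports, and on no further testing being done under the discretionary clause. The primary endpoint is unaffected. It should be corrected because the summary bears on safety and the correction is cheap.

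A smaller, separate point: the CSF and plasma trough plots in SAP 3.5.1 and 3.5.2.1 also end at Day 673, a telephone day, although the by-day tables cover later troughs.

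**What to change.** In SAP 3.5.2.3:
- Delete Days 421, 589 and 673.
- Add Days 442, 568, 694, 820, 946, 1072 and 1198.
- Keep the Day 505 predose sample as an additional test.
- Add the Day 1352/ET plasma sample that Appendix C already schedules, so that the post-treatment period has data.

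The list becomes 12 + 1 + 1 = 14 days: 1, 85, 169, 253, 337, 442, 505, 568, 694, 820, 946, 1072, 1198 and 1352/ET. If testing is to be staged, name the days in each batch and assign overall-period status only after the last one. Reconcile Appendices A and C on whether plasma for drug concentration is drawn at the seven visits. Extend the trough plots to Day 1261.

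The cost is a text edit plus 7 + 1 = 8 further samples per subject, or 8 × 20 = 160 at 20 subjects. These are samples, not assay runs: a positive screen also needs confirmation and a titer. The protocol already schedules every sample, so there are no new visits or draws, and Appendix C permits pharmacokinetic samples to be used for immunogenicity. The Day 505 and Day 1352/ET tests assume that enough plasma remains from the 0.35 mL blood collections.

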### **3.4.2     *Treatment***

Subjects who meet the eligibility criteria will be admitted to the study center on Study Day 1, undergo pre-dose evaluations, and then receive an LP injection of Study Drug (ISIS 396443). The subject will remain at the study center for at least 24 hours post-injection for safety monitoring and laboratory specimen collection. Subjects will return to the study center on Days 15, 85, 253, 379, 505, 631, 757, 883, 1009, 1135, and 1261 for follow-up evaluations and subsequent injections. Following LP injections on Study Days 15, 85, 253, 379, 505, 631, 757, 883, 1009, 1135, and 1261 subjects will not stay overnight in the hospital but will be monitored for at least 6 hours post-injection before leaving the study facility. A CSF sample will be taken pre-dose on each injection day for safety and Pharmacokinetic (PK) analyses. During the treatment period, the study center will monitor the subject's condition through safety monitoring visits on Study Days 16, 29, 86, 92, 169, 254, 337, 442, 568, 694, 820, 946, 1072, and 1198, and by telephone contact on Study Days 8, 43, 57, 71, 106, 127, 134, 148, 189, 197, 218, 239, 274, 295, 316, 358, 380, 400, 421, 463, 484, 506, 526, 547, 589, 610, 632, 652, 673, 715, 736, 758, 778, 799, 841, 862, 884, 904, 925, 967, 988, 1010, 1030, 1051, 1093, 1114, 1136, 1156, 1177, 1219, 1240, 1262, 1282, 1303, and 1324 (i.e., approximately every 3 weeks).

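### Subject antibody status is not defined relative to the Day 1 pre-dose result, so persisting pre-existing reactivity is pooled with new positivity and an infant positive only before dosing cannot be classed as negative

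*SAP*

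**What the plan says.** All the rules are in SAP 3.5.2.3.

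- **Samples.** Testing is planned first for "samples collected only on Days 1 (predose only), 85 (predose only), 169, 253, 337, 421, 505, 589, and 673". Other PK samples may be tested later.
- **Positive.** A subject is antibody positive "if they have at least one confirmed positive sample result at any time during the treatment or post-treatment evaluation periods".
- **Negative.** A subject is antibody negative "if all evaluated IM sample results are antibody negative and they have at least one evaluable IM result from Day 85 or later".
- **Everything else.** The residual rule begins "Otherwise, a study subject will be given" and assigns the inconclusive status.
- **Reporting.** The reported quantities are set out as "The IM incidence and IM incidence rate at each evaluated study timepoint, and for the overall treatment and post-treatment evaluation period". Each status is given as a number and percentage of evaluated subjects. Titers of positive samples are listed for subjects classed as positive.
- **Use.** PK and selected safety and efficacy results "may be further summarized (stratified) by antibody status (antibody negative vs. positive subjects) and treatment". This is optional.

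The section has no category for pre-existing, treatment-induced or treatment-boosted antibody. It postpones the persistent/transient distinction but does not mention the pre-existing/new distinction. It does not say whether the Day 1 pre-dose sample falls inside the treatment period.

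**The concern.** A pre-dose antibody sample is useful mainly because it separates reactivity the infant already had from reactivity that appeared after the drug was given. The SAP collects and tests that sample, then assigns status by rules that make no such comparison. Two patterns are affected.

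1. Positive on Day 1 and positive later at an unchanged titer. The infant is antibody positive and enters the overall incidence alongside infants who converted on treatment.
2. Positive on Day 1 and negative at every later test. The infant has complete negative post-dose data but cannot be negative. Whether the label is inconclusive or positive depends on an undefined period boundary, so two programmers could report different incidences from the same data.

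The SAP handles other safety data differently. SAP 3.1.1 has a general definition of baseline as the last value available before the first dose. SAP 3.6.2 counts laboratory results as post-baseline only after the first dose. For linked adverse event records that straddle the first dose, SAP 3.6.1 counts the later record as treatment-emergent only if severity worsened. Antibody status has no equivalent rule.

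What is at stake is the reported immunogenicity incidence and any summaries stratified by status. Immunogenicity sits in SAP section 3.5, which SAP 3.1.4 includes in the interim analyses meant to feed regulatory submissions.

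**Working it through.** The SAP states no figure here to reproduce. The check applies its three rules literally to every pattern of results, under both readings of the period boundary. Post-dose means after the first dose. Every post-dose sample on the initial test list is from Day 85 or later, so one negative post-dose result from that list meets the Day 85 condition.

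| Day 1 pre-dose | Post-dose samples | Status if Day 1 is outside the treatment period | Status if Day 1 is inside it |
|---|---|---|---|
| + | any + | positive | positive |
| + | all − | **inconclusive** | **positive** |
| + | none | inconclusive | positive |
| − | any + | positive | positive |
| − | all − | negative | negative |
| − | none | inconclusive | inconclusive |
| missing | any + | positive | positive |
| missing | all − | negative | negative |
| missing | none | inconclusive | inconclusive |

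Rows 1 and 4 get the same status, although row 1 may show no change from baseline. Row 2 is never negative.

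**Can Day 1 be read as inside the treatment period?** Yes. Protocol 3.4.2, headed Treatment, describes the Day 1 pre-dose evaluations, and Protocol Appendix A puts the Day 1 pre-dose column, with its immunogenicity sample, under the Dosing header. The SAP does not settle it.

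**Size of one misclassification** (planned sizes from SAP 1.1, all subjects evaluated):
- Overall: 1/20 = 5 percentage points.
- Cohort 1: 1/4 = 25 percentage points.

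A row 1 infant adds this to the positive column under both readings. A row 2 infant adds it to the positive column only if Day 1 is inside the treatment period; otherwise the same amount moves from negative to inconclusive.

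**How likely is it to arise?** The documents give no pre-dose rate, so b is an assumption. The chance of at least one reactive infant among 20 is 1 − (1 − b)^20:
- b = 0: 0%
- b = 2%: 1 − 0.98^20 = 33%
- b = 5%: 1 − 0.95^20 = 64%
- b = 10%: 1 − 0.90^20 = 88%

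**Expected counts, illustration only.** Assume n = 20, a 5% induction rate among Day 1 negatives, and no titer rise in Day 1 positives; s is the share of Day 1 positives still positive after dosing. Truly induced = 20(1 − b)(0.05). SAP positives with Day 1 outside the treatment period = 20(1 − b)(0.05) + 20·b·s. Inconclusive through Day 1 alone = 20·b·(1 − s).

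| b | Truly induced | SAP positive, s = 1 | SAP positive, s = 0.5 | Inconclusive, s = 0.5 |
|---|---|---|---|---|
| 0 | 1.00 | 1.00 | 1.00 | 0 |
| 2% | 0.98 | 1.38 | 1.18 | 0.20 |
| 5% | 0.95 | 1.95 | 1.45 | 0.50 |
| 10% | 0.90 | 2.90 | 1.90 | 1.00 |

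If Day 1 is inside the treatment period, the SAP positives equal the s = 1 column whatever the true persistence.

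**The case against.** The strongest reply is that the SAP defines ever-positive status during the study, claims nothing more, and already shows the reader what is needed. Incidence is tabulated at each timepoint, so Day 1 reactivity is visible. Titers are listed for positive subjects, so with about 8 to 20 infants a row 1 case can be picked out by hand. Immunogenicity is not among the listed endpoints, no test or dosing decision depends on it, and stratification by status is optional.

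Most of this stands and limits the importance of the point. It does not remove the defect. A Day 1 incidence is an aggregate and changes neither any infant's status nor the overall incidence. The titer listing covers only subjects classed as positive, so a row 2 infant labelled inconclusive has no planned titer listing.

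A reader might also infer four stronger things, which the documents do not support:

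- *That status ignores Day 1.* It does not: a Day 1 positive alone blocks negative status. What is missing is a comparison with Day 1.
- *That the SAP presents its positives as drug-induced.* It does not use that term. The problem is pooling, not a false claim of causation.
- *That every pre-dose-positive infant inflates the positive incidence, or that a false incidence of 5 to 10% should be expected.* Inflation needs reactivity to persist, or Day 1 to count as treatment period, and the size depends on a rate the documents do not give.
- *That the stratified summaries necessarily inherit a wrong label.* An inconclusive infant is left out of both strata, which loses a subject without mislabelling one.

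**Conclusion.** The point holds in a limited form. Persisting pre-existing reactivity and new positivity share one status, and an infant positive only before dosing is never negative despite clean post-dose data. This is a stated rule that yields an uninformative or wrong label, together with an undefined period boundary that makes one label indeterminate.

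If the pattern occurs, one infant counted as positive is worth 5 points overall at n = 20 and 25 points in Cohort 1 at n = 4. Whether it occurs rests on a pre-dose rate absent from the documents; at zero nothing changes. The effect is confined to a descriptive secondary output and any optional stratified summaries. It is worth correcting because the sample that resolves it is already planned.

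**What to change.** State in SAP 3.5.2.3 that the Day 1 pre-dose sample is baseline and lies outside the treatment period, and that post-dose means after the first dose. Then assign each infant to exactly one category:

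1. **Treatment-emergent positive:** Day 1 negative with at least one confirmed post-dose positive, or Day 1 positive with a post-dose titer rise of at least a pre-specified fold.
2. **Pre-existing, not treatment-emergent:** Day 1 positive and at least one post-dose positive, with no such rise shown.
3. **Negative:** all post-dose results negative, with at least one from Day 85 or later. Flag any Day 1 positive separately.
4. **Positive, baseline unknown:** Day 1 missing and at least one post-dose positive.
5. **Inconclusive:** all others, including infants with no evaluable result from Day 85 onward and no post-dose positive.

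The fold should come from the assay's dilution scheme and be fixed before results are seen. The documents do not describe that scheme, so no particular value can be taken from them.

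List titers for all Day 1 positives whatever their final status. Report the overall incidence by these categories. Use treatment-emergent status for any stratified summary and state how many infants that comparison leaves out.

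The cost is SAP wording, a small programming change and one extended listing. The Day 1 samples and antibody testing are already planned; titers would be reported for any Day 1 positive not already covered by the listing.
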